Aim 4b: To examine individual factors that may differentially influence response to one treatment versus another. Initial motor ability, cognition, somatosensation, intensity of both in-clinic and home-based motor practice, treatment compliance, age, and chronicity will be examined as potential moderators of motor outcome.

II. Background and Rationale

CI therapy is a highly efficacious motor rehabilitation therapy for stroke or hemiparesis of other etiologies. It has been shown to substantially increase the amount of use of an affected upper extremity ⁵⁻⁷ and to promote structural and functional brain plasticity. ⁸⁻¹² CI therapy is distinctive from traditional rehabilitation in several ways. 1) It involves a highly compressed and intensive training schedule (training of the more impaired arm on functional tasks for 3 hours daily for 10 consecutive weekdays). 2) CI therapy incorporates restraint of the less-impaired (i.e., "good") hand for a target 90% of waking hours. Restraint is delivered via a padded mitt that discourages the patient to engage in compensatory behavior with the less affected arm ^{13,14} and teaches the patient to use the more-affected (i.e., "bad") arm for daily activities. 3) CI therapy utilizes a number of behavioral techniques termed the "transfer package." The transfer package was designed to facilitate transfer of therapeutic

gains to real world activities, thereby enabling the patient to overcome the conditioned suppression of movement (e.g., learned nonuse) characteristic of chronic hemiparesis. ^{13,14} Transfer package techniques include daily monitoring of life situation use of the more affected arm via daily administration of the Motor Activity Log (a structured interview that monitors use of the more-impaired arm for 28 daily activities), providing feedback on patient progress, and problem-solving with the therapist to overcome perceived barriers to using the extremity.

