Measures will be administered within a week prior to beginning treatment, in the week following treatment, and at 6-month follow-up (±1 month). A rehabilitation professional blinded to treatment condition will perform the testing. Reliability of the blinded assessors will be monitored by videotaped assessments reviewed by independent raters.

Additional quality metrics that could create apparent differences in effectiveness in clinical populations will also be measured. After completion of participation, we will survey participants to collect qualitative feedback regarding their experiences with the treatment. Participants will be asked about which therapy condition (traditional CI therapy, gaming CI therapy, standard therapy) they would have preferred under ideal (i.e., cost and transportation are not an issue) and realistic (i.e., their current resources are a consideration) conditions. Differential adherence will also be examined by the proportion of therapy sessions attended, hours of mitt use objectively quantified by a sensor in the mitt, hours of game play, and self-reported compliance with home practice.

Outcome measure	Addresses	Pre	Post	6mo
Motor Activity Log	Nonuse for daily activities	X	X	X
WMFT	Motor speed/function	X	х	X
Grip strength of WMFT ⁹⁹	Weakness	Х	х	X
Kinematics	Weakness, range of motion, motor control, ataxia, poor precision, speed, hypertonicity	х	Х	X
Neuro-QOL	Quality of Life	Х	X	X
Activity monitoring	Nonuse for daily activities	Х	X	X
Brief Kinesthesia Test	Sensory proprioception	Х	х	X
Touch Test Monofilaments	Tactile loss	Х	х	X
Montreal Cognitive Assessment (MoCA)	Cognitive screen	Х		

Survey		X	

Recruitment

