The current proposal aims to conduct a multi-site randomized controlled trial comparing virtual-reality gaming delivery of CI therapy with (1) traditional clinic-based CI therapy of equal total duration and (2) a control group equating the dose of in-person therapy. Individuals with chronic stroke will be randomized to one of four different interventions: (1) traditional clinic-based CI therapy (35 therapist/client contact hours), (2) therapist-as-consultant virtual reality CI therapy (5 therapist/client contact hours in the clinic and 15 hours of independent game play at home), (3) therapist-as-consultant virtual reality CI therapy with additional therapist contact via telerehabilitation (5 therapist/client contact hours in the clinic, 6 brief contacts via teleconference, and 15 hours of independent game play in the home), and (4) 5 hours of standard occupational therapy. After 6-month follow-up, individuals assigned to standard OT/PT will cross over to a modified gaming therapy condition (a stand-alone application of the rehabilitation game without additional therapist contact). This crossover design is ethically responsible and will enable the team to test the feasibility and initial efficacy of a completely stand-alone implementation of the game, as well as to determine the effect of varying amounts of therapist contact on game-based rehabilitation outcomes (group 2 vs group 3 vs group 4 crossed over).

Table: Timeline of Participation

STUDY		THERAPY (weeks 2-4)			THERAPY	
ARM	Pre-tx	, , ,	Post-tx	6 month		
CI therapy	testing,	35 face-to-face hours, 15	testing,	follow-up		
	week 1	spent in active motor	week 5	testing		
		practice				
CI therapy		5 face-to-face hours, 15				
gaming (2)		hours in-home gaming				
CI therapy		5 face-to-face hours, 2.6				
gaming (3)		teleconsultation hours, 15				

	hours in-home gaming			
Standard	5 face-to-face hours		15 hours in-	Post-
care			home gaming	gaming
				testing

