Group 1, Traditional CI therapy: We will employ a 35-hour "dose" of CI therapy in the current trial. All elements of traditional CI therapy will be provided. Treatment will consist of 35 therapist/client contact hours in the clinic, over the course of 3 weeks. Delivery of the "transfer package" will occur during the other 5 hours and will include the following elements: (1) establishing a behavioral contract (in which goals for the intervention are set, the therapist secures the client's "buy in," a plan for increased use of the more affected upper extremity in the home setting is drafted, and a schedule of mitt use is established), (2) daily administration of the Motor Activity Log (self-assessment of weaker arm use for daily activities), (3) a daily diary of new activities attempted at home is reviewed, and (4) problem-solving to overcome barriers to use of the more affected upper extremity is conducted. In addition, the client will agree to wear a padded restraint mitt on the less affected hand for the majority of waking hours to encourage use of the weaker hand for daily activities. The restraint mitt is equipped with a sensor to provide the participant with feedback on how long he/she has worn the mitt. Finally, the participant will agree to 30 minutes per day of individualized task-practice outside the clinic (in addition to training in the clinic) focused on functional activities catered towards accomplishing the person's therapeutic goals.

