Group 2, Gaming CI therapy. This intervention is designed such that physical/occupational therapists manage patients in a consultative role, thus allowing more patients to be served. 5 therapist/client contact hours will occur in the clinic on approximate treatment days 1, 3, 6, and 11 and will focus on treatment elements that cannot be readily addressed through the game (e.g., transfer package with guided problemsolving). The first session with the therapist (2 hours) will involve establishing the behavioral contract, reviewing the Motor Activity Log (from pre-test) with guided problem-solving, and customizing the game to the participant. Thereafter, sessions will focus on review of progress with the home program, modifying game customization as needed, and on treatment elements that cannot be readily addressed through the game (e.g., guided problem-solving portion of the transfer package with ADL practice as needed, establishing home skill assignments collaboratively). Matching the CI therapy delivery schedule, 15 hours of progressive massed motor practice will occur through in-home video game play over 3 weeks. Participants will play the game during times of their choosing. The proposed delivery system thus allows patients access to rehabilitation between episodes of care provided by therapists. This distribution of activities amounts to the same amount of active motor practice as CI therapy (15 hours) and 5 hours of "transfer package" activities, equivalent to that of traditional CI therapy. In lieu of the mitt, the participant will wear an activity monitor biofeedback device for the majority of waking hours. As with traditional CI therapy, the client will agree to an additional 30 minutes per day of individualized task-practice.

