Neuromuscular re- education	(20 minutes) Level: Activities completed: Intensity easy moderate hard	(10 minutes) Level: Activities completed: Intensity easy moderate hard	(10 minutes) Level: Activities completed: (10 minutes) lntensity easy moderate hard	(10 minutes) Level: Activities completed: Intensity easy moderate hard	
Functional Training (one of each: dexterous, reaching close, far, high as possible)	(25 minutes) Activities completed: 1. 2. 3. 4.	(25 minutes) Activities completed: Intensity easy moderate hard	(25 minutes) Activities completed: Intensity easy moderate hard	(25 minutes) Activities completed: Intensity easy moderate hard	
Progressive Strengthening	(25 minutes) Activities completed: Intensity easy Moderate hard	(15 minutes) Activities completed: Intensity easy moderate hard	(15 minutes) Activities completed: Intensity easy moderate hard	(15 minutes) Activities completed: Intensity easy moderate hard	
Teach, review home program (Shoulder strengthening Theraband GRASP, Pang, 2006	flexion (20 minutes) abduction extension external rotation (progress resistance of band and increasing repetitions as appropriate targeting 30 min of exercise at Borg level 4).		(10 minutes) Review and update HEP	(10 minutes) Review and update HEP	

Assessment Measures

WOLF MOTOR FUNCTION TEST DATA COLLECTION FORM

Participant ID:		Date:	Site:	
Test (check one): Pre-tre	eatment	Post-treatment_	6 month follow-up _	
Affected arm (circle one): Right	Left		
Task	Unaffect	ted Arm Time (min:sec	c) Affected Arm Time (n	nin:see)
1. Forearm to table (side)				
2. Forearm to box (side)	_			
3. Extend Elbow (side)				
4. Extend Elbow (weight)				
5. Hand to table (front)				
6. Hand to box (front)				
7. Weight to box		lbs.	lbs	
8. Reach and retrieve				
9. Lift can				
10. Lift pencil	_			
11. Lift paper clip				
12. Stack checkers				
13. Flip cards	_			
14. Grip strength	kgs,	_kgs,kgs.	kgs,kgs,	_kgs.
15. Turn key in lock				
16. Fold towel				
17 Lift basket				

Motor Activity Log (UE MAL) Score Sheet

Amount Scale How Well Scale

1.	Turn on a light with a light switch		 if no, why? (use code) Comments
2.	Open drawer		 if no, why? (use code)
3.	Remove an item of clothing from a drawer		 if no, why? (use code)
4.	Pick up phone		 if no, why? (use code)
5.	Wipe off a kitchen counter or other surface		 if no, why? (use code)
-	Get out of a car (includes only the movemen body from sitting to standing once the door is open).		 if no, why? (use code)

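### Aim 4b treats practice intensity and treatment compliance, both observed after randomisation, as moderators of treatment response; comparing arms at a given level of either is not a randomised comparison and can mislead

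*Combined protocol and SAP*

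**What the plan says.** Section I (Objectives), Aim 4b, sets out to "examine individual factors that may differentially influence response to one treatment versus another". Its candidate list opens with initial motor ability, cognition and somatosensation and continues: "intensity of both in-clinic and home-based motor practice, treatment compliance, age, and chronicity will be examined as potential moderators of motor outcome".

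The Measurement/Instrumentation section plans a separate look at differential adherence, using the proportion of sessions attended, "hours of mitt use objectively quantified by a sensor in the mitt, hours of game play, and self-reported compliance with home practice". All of these accumulate during treatment.

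Under Detailed Study Procedures, the Group 2 description replaces the restraint mitt: "In lieu of the mitt, the participant will wear an activity monitor biofeedback device for the majority of waking hours". Group 3 receives the same treatment with added video consultations. Group 4 has no mitt, and it plays the game only after crossing over at 6 months.

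The Data Analysis paragraph specifies mixed models with treatment, time and their interaction as fixed effects and subject as a random effect. It contains no moderator term, does not separate baseline from post-randomisation factors, and names no causal method for the latter.

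**The concern.** A moderator in the sense of Aim 4b's first sentence is a patient characteristic across whose levels the difference between therapies varies. For a characteristic fixed before allocation, randomisation still holds within each level. For practice intensity and compliance it does not. The patients who comply with 35 clinic hours and a mitt need not resemble those who comply with 5 clinic hours and 15 hours of game play at home. The plan itself allows that adherence may differ by arm, since it intends to examine exactly that.

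Aim 4b is meant to inform the choice of therapy. A treatment-by-compliance result could reflect who complies in each arm rather than who benefits more. A patient choosing a therapy also knows their age and impairment but not their future compliance.

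**Working it through.** **1. Timing of the seven factors.** Motor ability, cognition, somatosensation, age and chronicity can all be taken at the pre-treatment visit. Practice intensity and compliance cannot be known before treatment starts.

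**2. Availability by arm in the randomised period.**

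| Measure | Group 1 | Groups 2–3 | Group 4 |
|---|---|---|---|
| Mitt hours | yes | no | no |
| Game hours | no | yes | no |
| Sessions attended | yes | yes | yes |
| Self-reported home practice | yes | yes | yes |

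Mitt and game hours cannot enter a four-arm interaction. Attendance and self-reported home practice can, but the comparison is then non-randomised. This step needs no assumed values.

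**3. When the comparison is distorted.** The plan has no figure to reproduce: it gives no sample size, alpha, correlations or moderator model. Every input here is assumed. Let a prognostic trait correlate *r* = 0.5 with gain (SD 1). Let it correlate *g* with compliance (SD 1 within arm), with no true moderation. Then:

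- bias in the arm contrast at fixed compliance = *r* × *g* × (gap in mean compliance);
- false interaction slope between two arms = *r* × (difference in *g*).

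Bias for Group 2 minus Group 1 if Group 2 has the lower mean compliance, in SD of gain. The formula value comes first and a simulated value (60 per arm, 2,000 trials) follows in brackets:

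| Gap in mean compliance (SD) | g = 0.3 | g = 0.5 | g = 0.7 |
|---|---|---|---|
| 0 | 0 (0.001) | 0 (−0.003) | 0 (0.002) |
| 0.25 | 0.0375 (0.042) | 0.0625 (0.064) | 0.0875 (0.089) |
| 0.5 | 0.075 (0.070) | 0.125 (0.124) | 0.175 (0.172) |
| 1.0 | 0.15 (0.152) | 0.25 (0.249) | 0.35 (0.349) |

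The sign reverses if Group 2 complies better. For the interaction, *g* = 0.7 in one arm and 0.3 in another gives 0.5 × (0.7 − 0.3) = 0.20. A large two-arm simulation gave 0.195 to 0.206.

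**4. False-positive rate.** This is a nominal 5% test of treatment-by-compliance on the pre-to-post change across four arms, with 4,000 simulated trials per setting:

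| g in Groups 1/2/3/4 | 40 per arm | 60 per arm | 100 per arm |
|---|---|---|---|
| 0.5 in all | 4.9% | 5.5% | 5.0% |
| 0.5/0.3/0.3/0.3 | 6.7% | 7.8% | 9.6% |
| 0.3/0.5/0.5/0.3 | 7.0% | 8.8% | 12.1% |
| 0.5/0/0/0 | 19.0% | 25.8% | 41.0% |

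If the trait affects only the level of the outcome and not the gain, the rate stays at 4.3–5.6% under every pattern of links examined.

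**The case against.** The strongest reply is that the plan specifies no treatment-by-compliance test, so the criticism is of an analysis nobody has written down. The phrase about moderators of motor outcome could mean prediction within each arm. That reading is possible, but the documents do not state it, and the aim's opening sentence concerns one treatment versus another. What stands is that the plan does not commit to the distorted analysis in detail. It names the two factors for that purpose and sets no limit.

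The figures are also only illustrative. They need one compliance variable on a common scale, so at most they apply to attendance and self-reported home practice. The 19–41% row requires a link in one arm and exactly none in the other three. A reader might infer that the trial will produce false moderators at such rates. The documents do not support that.

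Three other inferences go too far:

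- **Group 1 practice time.** A reader might see three rival figures. The CI therapy Description of Therapy gives 3 hours × 10 days = 30 hours. The Group 1 text says transfer-package delivery "will occur during the other 5 hours and will include the following elements", and 30 + 5 = 35 contact hours, so these two agree. The 15 hours in the timeline table, repeated under Group 2, is the active part. Only its relation to the 30 hours needs clarifying.
- **Somatosensation.** The timing rule is "Measures will be administered within a week prior to beginning treatment, in the week following treatment, and at 6-month follow-up", and the sensory tests are scheduled at all three visits. One might infer that post-treatment scores will serve as moderators. The word initial at the head of the list can govern somatosensation too, so this is only an ambiguity.
- **In-clinic practice in Groups 2–3.** The lack of a practice count on those checklists is not an omission. The design assigns motor practice to the game at home and clinic time mainly to the transfer package.

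**Conclusion.** The concern holds as a matter of principle. As worded, Aim 4b would have therapies compared within levels of two post-randomisation factors, and nothing in the Data Analysis text prevents it. Two of the adherence measures cannot be compared across the four arms at all.

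Confidence in the principle is high; confidence in any size is low. Distortion requires that prognosis predicts gain, that compliance is linked to prognosis, and that either mean compliance or that link differs by arm. If mean compliance and links are equal across arms, or the trait affects level only and change is analysed, it is nil. Within the assumed ranges above, the bias runs from 0 to 0.35 SD of gain.

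A reader might infer that the trial's main result is compromised. It is not: the treatment-by-time comparison does not condition on intensity or compliance. The point concerns a secondary subaim, and it is worth correcting because the correction is cheap.

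**What to change.** Reword Aim 4b so that the moderators are the pre-treatment values of motor ability, cognition, somatosensation, age and chronicity. In Data Analysis, add treatment-by-factor-by-time terms for these, labelled exploratory, and report the number of tests. Five factors on two primary outcomes make ten tests. At 5% each, and if independent (an assumption), the chance of at least one false positive is 1 − 0.95^10 ≈ 40%.

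Report practice intensity and compliance by arm under the differential-adherence examination already planned. If they are modelled, do so only within arm or as mediation, labelled non-randomised and exploratory.

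Two side points, not needed for the argument, also bear on how compliance would be scored. The Group 4 description prescribes stretching as home practice, whereas the Usual Care treatment materials prescribe theraband strengthening; these must be reconciled. For Group 1, state how the 15 active hours relate to the 30.

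The cost is a wording change, a few sentences of analysis text and these two text checks, with no new data. The downside is two fewer candidate moderators.

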The transfer package is perhaps the most revolutionary element of CI therapy in that it leverages psychological theory to induce behavioral change. Patient gains in real-world arm use are reduced by approximately 67% when it is omitted from the CI therapy protocol. ¹² Furthermore, patients fail to demonstrate the brain reorganization that is typical of CI therapy in the absence of the transfer package. ¹² Behavior-monitoring and problem-solving elements (strongly emphasized by the transfer package) are present in most empirically-validated psychological interventions that target behavior change and their importance to the field of physical rehabilitation is becoming increasingly apparent. Traditional approaches to motor rehabilitation that heavily emphasize strength, speed, or "normalcy" of movement (i.e., motor training only), and do not incorporate elements of the transfer package, often yield motor gains that do not translate into improved function for the patient (i.e., the patient still operates unimanually at home). Through use of the transfer package, CI therapy patients regain their ability to use both arms for daily tasks, enabling them to retain motor gains over time.

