Individuals with chronic stroke will be randomized to one of four different interventions: (1) traditional clinic-based CI therapy (35 therapist/client contact hours), (2) therapist-as-consultant virtual reality CI therapy (5 therapist/client contact hours in the clinic and 15 hours of independent game play at home), (3) therapist-as-consultant virtual reality CI therapy with additional therapist contact via telerehabilitation (5 therapist/client contact hours in the clinic, 6 additional brief teleconference sessions, and 15 hours of independent game play in the home), and (4) 5 hours of standard occupational therapy. The clinic-based CI therapy arm is the "gold standard" against which gaming therapy is compared (group 1 versus group 2 and group 3). The comparison to standard care (group 2 versus group 4) will demonstrate whether game-based treatment between therapy sessions enhances motor outcomes. The comparison between groups 2 and group 3 will determine the extent to which additional therapist monitoring via video conference improves treatment response of a home-based intervention. Motor function (Wolf Motor Function Test) and daily use of the more affected hand (accelerometry) will be measured prior to treatment, after treatment, and 6 months later.

Sample & Inclusion/Exclusion Criteria

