- 2. Only record the required activities for review for each session, turning the camera off after each activity
- 3. Complete Treatment Received Form
- 4. Review 4 components of intervention: intensive practice through game, computerized MAL, smart watch, Transfer Package of carry-over techniques. Emphasize that the game is only part of the therapy and that the other components are at least as important. The other components drive the brain plasticity. (~10 min)
- 5. Instruction in game play and customization of game to individual. (~30 minutes)
 - Occurs in home on participants' own schedule.
 - 1.5 hours per day on 10 treatment days. Participants are encouraged to break this down into at least 3 separate play sessions per day (15-30 min sessions are optimal).
 - Tell the participant to record their amount of game play each day on the Game Log
 - Write down the randomly generated Game ID on one of the site business cards and instruct the participant to keep this with them and bring it to every visit (this is how you will access their game data)
 - Instruction on hot spot set-up
- 6. Instruction in use of smart watch (~5 min). Have client record the daily count on the **Limb** Activation Log each night before going to bed
- 7. Introduce the **Treatment Contract** by reading/explaining each component of the therapy. Briefly present the research. (15 min)
 - discuss the need for massed practice with the weaker arm and limited use of the stronger arm to drive brain plasticity.
 - discuss how quality of life improvements relate directly to the amount of use for daily activities, regardless of motor ability.

- 8. **Home Achievement Record** portion of Treatment Contract. (45 min)
 - Compile list of daily activities done on both weekdays and weekends (one list)
 - Photocopy daily activities list prior to categorizing level of involvement of the weaker arm in each task (10 copies). Provide 1 copy to client to complete prior to next session.
 - Discuss involvement of the weaker arm in each task with problem-solving.
- 9. Explain the **Home Skill Assignment List (HSA)** and select 10 items (15 min)
- 10. Ask participant if he/she watched the CIMT videos on YouTube. If he/she has not, assign as homework.
- 11. Ask participant about adverse events and fill out **Adverse Event Reporting Form** if need be
- 12. Add comments to Therapist Treatment Recording Log
- 13. Store the video on the encrypted hard drive under the correct group and session subfolder

Game Play

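### Group 2 v Group 4 compares two whole treatment packages, so it cannot show what game play between sessions adds

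*Combined protocol and SAP*

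**What the plan says.** The Research Design section gives Group 2 v Group 4 a specific purpose: the comparison "will demonstrate whether game-based treatment between therapy sessions enhances motor outcomes". Detailed Study Procedures describes Group 4 as "a control group equating the dose of in-person therapy".

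The treatment descriptions show what each arm receives. In the Group 2 section, the clinic hours "will focus on treatment elements that cannot be readily addressed through the game", and the first, two-hour session "will involve establishing the behavioral contract, reviewing the Motor Activity Log (from pre-test) with guided problem-solving, and customizing the game to the participant". That section describes the clinic time as five hours of transfer package, the same as in traditional CI therapy. The Self-Gaming checklist tells therapists on day 1: "Emphasize that the game is only part of the therapy and that the other components are at least as important". The Group 4 section and the Usual Care materials describe conventional upper-limb therapy with a home exercise programme.

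**The concern.** The phrase about treatment between sessions points to home play. Crediting a Group 2 v 4 difference to home play requires arms that are alike apart from the game. If they also differ in clinic content and behavioural components, any difference could come from those, from the game, or from both.

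At stake is what the trial may conclude. A positive result, read as the sentence invites, would say that adding a home game to ordinary therapy sessions improves motor outcome. Nobody in the trial is randomized to that combination. The reading would also sit badly with the protocol's own rationale, which places great weight on the transfer package.

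**Working it through.** The documents give no sample size, effect size or other figure for this contrast, so there is none to reproduce. The check compares the two arms component by component.

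**What matches**
- Therapist hours. Group 2: 2 + 1 + 1 + 1 = 5 h (in-clinic treatment schedule). Group 4: 120 + 3 × 60 = 300 min = 5 h (Traditional Rehabilitation Protocol).
- Visit schedule. Both arms attend on about days 1, 3, 6 and 11.
- Nominal daily home practice apart from the game. Group 2: 30 min of individualized tasks. Group 4: 2 × 15 = 30 min of exercise, except on clinic days (Traditional Rehabilitation Protocol).

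**What differs**

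| Component | Group 2 | Group 4 |
|---|---|---|
| Home game play | 1.5 h × 10 days = 15 h | None before crossover |
| Clinic content | Transfer package and game set-up | Evaluation, re-education, functional training, strengthening, home programme |
| Treatment contract | Yes | Not in materials |
| Home Achievement Record | Yes | Not in materials |
| Home skill assignments | Yes, 10 items | Not in materials; exercise instead |
| Feedback watch | Yes, target 10 h/day on the weaker arm | Not in materials |
| Weekly MAL after treatment | 4 weeks | Not in materials |

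The last row matters because the MAL is listed as a primary measure under Measurement/Instrumentation.

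**Clinic minutes**
- Group 2, day 1 (Self-Gaming checklist): overview 10 + game instruction and customization 30 + watch 5 + contract 15 + Home Achievement Record 45 + home skill assignments 15 = 120 min. Game set-up is 30/120 = 25%. No item is listed as re-education, strengthening or functional training.
- Group 4, all visits (Traditional Rehabilitation Protocol tables): evaluation 25; re-education 20 + 3 × 10 = 50; functional training 4 × 25 = 100; strengthening 25 + 3 × 15 = 70; home programme 25 + 3 × 10 = 55. Total 300 min. The Group 4 checklist and log put day 1 at evaluation 30 and home programme 20; the total is unchanged.

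**Does another arm isolate the game?** To do so, an arm would need Group 4's content plus the game, or Group 2's content without it. Group 3 has the game, as Group 2 does, and adds teleconferences. Group 1 replaces game practice with in-clinic practice and the watch with a mitt. Neither qualifies. Group 4's later crossover to gaming has no concurrent randomized control and starts after the 6-month follow-up. The mixed model in Data Analysis tests treatment by time across the four arms and has no term that separates components.

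**The case against.** The strongest defence is that this is a legitimate comparative-effectiveness trial of packages. Aim 4 is framed as a delivery model of CI therapy against standard care, the control is described as matching in-person dose, and the model is the same whichever wording is used. If game-based treatment is read as the whole gaming package, the sentence is loose rather than false. The package framing does stand, and it supports the fix. It does not remove the sentence, which refers to treatment between sessions while the content within sessions also differs.

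Four stronger readings are tempting but unsupported.

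- **That only contact hours are equal.** Visit schedule also matches, and nominal home-practice minutes nearly do. Group 4 also has functional practice with verbal encouragement to use the weaker arm.
- **That the computerized MAL used during treatment is a further confounder.** The protocol describes the automated MAL and its problem-solving module as part of the game. Only the MAL sent by survey or mail after treatment lies outside it.
- **That about two-thirds of a Group 2 v 4 difference would arise without the game.** The Background says: "Patient gains in real-world arm use are reduced by approximately 67% when it is omitted from the CI therapy protocol". That concerns omission from CI therapy, and real-world arm use rather than Wolf Motor Function Test time. Suppose that it carried over to gaming. Set the full-package gain to 1, the gain without the transfer package to 0.33, and Group 4's gain to g. The transfer-package share of the difference is then 0.67/(1 − g): 67%, 74%, 84% or 100% for g = 0, 0.1, 0.2 or 0.33. Every value of g is assumed, so the figure gives no bound here.
- **That the contrast would wrongly support the stand-alone game.** The protocol assigns that question to the Group 4 crossover, not to Group 2 v 4. The crossover's own limits are a separate matter.

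**Conclusion.** The concern holds as a fault in the stated inference. Group 2 v Group 4 is a valid randomized comparison of the gaming CI therapy package with standard therapy at equal therapist hours and on the same visit schedule. It cannot show whether game play between sessions enhances motor outcomes, because clinic content, treatment contract, Home Achievement Record, home skill assignments, feedback watch and post-treatment MAL differ too, and no randomized arm separates them.

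No size can be put on the error: the share of any difference due to the game is not identifiable from this design. The conclusion rests on the arms being delivered as the treatment materials describe, and on an item missing from Group 4's checklist, log and protocol not being given.

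**What to change.** Replace the sentence in Research Design with:

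> Group 2 v Group 4 estimates the effect of the gaming CI therapy package (game, transfer package, feedback watch, home task practice) v standard therapy with equal therapist hours and visit schedule.

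Drop the attribution to between-session game play there and in any report of the contrast. Game hours are already recorded, and Aim 4b already plans to examine practice intensity and compliance. Label any association of logged game hours with outcome in Groups 2 and 3 as exploratory, since hours played are not randomized.

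This costs wording only: no added participants, data or procedures. The downside is a narrower claim.

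Separately, reconcile the descriptions of Group 4. Its home practice is stretching in the protocol's Group 4 section but resistance-band strengthening in the Usual Care materials. The clinic-time split also differs: 60 min resistance exercise, 120 re-education and 120 functional practice in the former, against 70, 50 and 100 plus evaluation and home-programme time in the latter. The package being compared should have one description.
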